12.0 STATISTICAL CONSIDERATIONS

12.1 Study design overview

This is a multi-center, single arm phase 1/2 study of pembrolizumab plus pralatrexate for patients with relapsed/refractory PTCL. Patients will receive 21-day cycles of the combination therapy up to 2 years until disease progression, unacceptable toxicity, or until the patient meets any criteria for removal from protocol therapy in [Section 5.10](#), whichever is earlier. Response will be assessed every 4 cycles. The phase 1 dose-escalation portion of the study, with 2 dose levels and 1 possible de-escalation dose level ([Table 5.3](#)), will determine the MTD and the RP2D of the combination therapy. After the completion of the phase 1 portion, additional patients will be enrolled and treated at the RP2D in the Phase 2 portion. Another primary endpoint is overall response rate per the Lugano classification.⁸ Secondary endpoints include CR rate, duration of response, overall survival, progression-free survival, ORR and CR rate per the International Harmonization Project response criteria (Cheson 2007)⁹ and response status based on LYRIC criteria¹⁰.

12.1.1 Phase 1 design

During the Phase 1 portion of the study, a modified, more conservative version of the Rolling 6 design of Skolnik et al will be employed.⁸⁷ In this design, at most, 3 patients will be under observation for DLT on the current test dose level at any time. DLT observation period is 2 cycles (defined in [Section 5.5](#)). DLTs are defined in [Section 5.5](#). Patients who are not evaluable for DLT (defined in [Section 5.7](#)), i.e., those who did not receive the doses of pembrolizumab during DLT period (not due to DLT) or those who missed any doses of pralatrexate during DLT period (not due to DLT), will be replaced. Once 3 patients are evaluable

with no patient at that dose level experiencing a DLT, the dose can be escalated, or up to 3 additional patients may be treated at the current dose level. No more than 6 evaluable patients will be accrued to any dose level. Escalation will terminate as soon as ≥ 2 patients experience DLT at a given dose level. If 1/6 patients experience DLT at the current dose level, the dose will be escalated to the next higher level. If more than 1/6 patients experience DLT, then the next lower dose will be expanded. MTD will be declared the highest dose level at which 6 evaluable patients have been treated and, at most, 1/6 patients experience DLT. The MTD will be considered the RP2D, unless the PI chooses a lower dose level, based on toxicity in subsequent cycles.

These rules are outlined in the Table below.

Table 12.1.1. Dose Escalation Rules

# Patients on Current Level			Action
With DLT [^]	Evaluable	Evaluable + At Risk [^]	
0	0	1-2	Accrue next patient at this level*
0	0	3	Hold accrual
0	1	1-3	Accrue next patient at this level
0	1	4	Hold accrual
0	2	2-4	Accrue next patient at this level
0	2	5	Hold accrual
0	3-6	3-6	Accrue next patient at the next higher level* ^{*,+}
1	1	1-2	Accrue next patient at this level
1	1	3	Hold Accrual
1	2	2	Accrue next patient at this level
1	2	3-4	Hold accrual
1	3-5	3-5	Accrue next patient at this level
1	3-5	6	Hold accrual
1	6	6	Accrue next patient at the next higher level*
2**	any	any	Accrue next patient at next lower level (max 6)

[^]: DLT: a patient with a documented DLT

Evaluable: a patient who is either fully evaluable for toxicity for the purpose of dose escalations or has a DLT

At Risk: a patient who is on treatment and has not yet passed the evaluation period nor had a DLT

^{*}: During the dose-escalation portion, if higher dose level is already closed, the next lower dose will accrue to a total of 6 patients, with 2 or higher DLTs requiring further dose de-escalation.

⁺: Although under this scenario escalating to the next higher dose level is suggested, additional patients can be accrued to the current level -up to n=6 patients.

^{**}: Patients treated on a higher dose will have their treatment modified to the dose below the dose level with 2 DLTs, if pending patients have DLT.

12.1.2 Phase 2 Design

In the phase 2 portion, patients will be treated at the RP2D. The phase 2 portion of this study will implement a Gehan two-stage design⁸⁸ to estimate the ORR and to evaluate the activity of the combination therapy. Patients treated during the Phase 1 portion at the RP2D will be included in the Phase 2 evaluations if they are evaluable for response, defined as patients who received at least 1 dose of pembrolizumab and at least 1 dose of pralatrexate and had at least 1 disease assessment ([Section 5.7](#)). The sample size is based on the desire to estimate the response rate with approximately 10% standard error, and early stopping if the combination is unexpectedly ineffective. In the pivotal PROPEL trial, the overall response rate (ORR) in 109 evaluable patients who received pralatrexate as a single agent was 29%, including 12 (11%) complete responses (CR) and 20 (18%) partial responses (PR).⁵

The phase 2 portion of the study is expected to evaluate a minimum of 7 and a maximum of 24 patients, including the patients treated at RP2D during the Phase 1 portion that are evaluable for response. At stage 1, if 0 responses are seen in the first 7 evaluable patients (including up to 6 patients enrolled during the Phase 1 portion that are evaluable for response), the study will be terminated and the true ORR will be declared $\leq 35\%$. If at least 1 patient responds, the trial will continue to the second stage. At stage 2, a total of 24 patients will be evaluated (including up to 6 patients enrolled during the Phase 1 portion that are evaluable for response).

This design provides for estimation of the response rate with approximately 10% standard error. The standard error will be 9.4%-10.2% after 24 patients if the ORR rate is 30%-70%. The maximum width of the 95% exact binomial confidence interval for ORR will be 42% after 24 patients. Under this design if the ORR is $>35\%$, there would be $\geq 95\%$ chance of at least one response among the first 7 patients.

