During the Phase 1 portion of the study, a modified, more conservative version of the Rolling 6 design of Skolnik et al will be employed. In this design, at most, 3 patients will be under observation for DLT on the current test dose level at any time. DLT observation period is 2 cycles. Patients who did not receive the doses of pembrolizumab during DLT period (not due to DLT), or those who missed any doses of pralatrexate during DLT period (not due to DLT) will be replaced. Once 3 patients are evaluable with no patient at that dose level experiencing a DLT, the dose can be escalated, or up to 3 additional patients may be treated at the current dose level. No more than 6 evaluable patients will be accrued to any dose level. Escalation will terminate as soon as \geq 2 patients experience DLT at a given dose level. If 1/6 patients experience DLT at the current dose level, the dose will be escalated to the next higher level. If more than 1/6 patients experience DLT, then the next lower dose will be expanded. MTD will be declared the highest dose level at which 6 evaluable patients have been treated and, at most, 1/6 patients experiences DLT. The MTD will be considered the RP2D, unless the PI chooses a lower dose level, based on toxicity in subsequent cycles.

Phase 2 portion

In the phase 2 portion, patients will be treated at the RP2D. The phase 2 portion of this study will implement a Gehan two-stage design to estimate the ORR and to evaluate the activity of the combined regimen. Patients treated during the Phase 1 portion at the RP2D will be included in the Phase 2 evaluations if they are evaluable for response, defined as patients who received at least 1 dose of pembrolizumab and at least 1 dose of pralatrexate and had at least 1 disease assessment. The sample size is based on the desire to estimate the response rate with approximately 10% standard error, and early stopping if the combination is unexpectedly ineffective. In the pivotal PROPEL trial, the overall response rate (ORR) in 109 evaluable patients who received pralatrexate as a single agent was 29%, including 12 (11%) complete responses (CR) and 20 (18%) partial responses (PR).⁵

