5.7 Replacement of Subjects

During the Phase 1 portion of the study, subjects will be replaced for any of the following:

- Missed any doses of pralatrexate during the DLT period (not due to DLT).
- Did not receive the doses of pembrolizumab during the DLT period (not due to DLT).

Subjects who are replaced for missed doses may continue to receive study treatment if there is clear clinical benefit, but will not be included in DLT analysis.

During the Phase 2 portion of the study, subjects who did not receive at least 1 dose of pembrolizumab and 1 dose of pralatrexate, or who did not have a tumor response assessment (except due to progression of disease prior to the first tumor response assessment) will be replaced. If a patient discontinues study treatment prior to the first response assessment due to progressive disease, the treating physician is encouraged to obtain imaging to confirm progression.

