12.3.3 Analysis of Anti-tumor Activity

This study will aim to obtain an estimate of the anti-tumor activity of the study combination. ORR will be calculated as the proportion of evaluable patients that have confirmed CR or PR, as defined according to the 2014 Lugano Classification, exact 95% confidence intervals will be calculated for these estimates. Response rates will also be evaluated based on number and type of prior therapy(ies). Duration of response, as well as progression-free survival and overall survival will be estimated using the product-limit method of Kaplan and Meier. As secondary endpoints, the ORR and CR rate will also be estimated according to the International Harmonization Project response criteria (Cheson 2007).⁹

Any patient treated at the RP2D, including those from the Phase 1 portion, will be included in efficacy analyses. Patients will be evaluable for efficacy assessment if they received at least one dose of pralatrexate and at least one dose of pembrolizumab and underwent at least one response assessment. As discussed in [Section 5.7](#), patients will be evaluable for efficacy if they discontinued study therapy prior to the first response assessment because of progression of disease rather than solely because of unacceptable toxicity, withdrawal of consent, or investigator's decision.

12.3.4 Safety Analysis and Stopping Rules for Excessive Toxicity or for Rapid Disease Progression

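### Section 12.1.2 and the synopsis omit the early-progression exception from the definition of evaluable for response, so the Gehan count (the first 7 and the 24) does not match the efficacy population in 12.3.3

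*Combined protocol and SAP*

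**What the plan says.** **Section 12.1.2 (Phase 2 Design).** The definition comes in the sentence that carries Phase 1 patients over: "Patients treated during the Phase 1 portion at the RP2D will be included in the Phase 2 evaluations if they are evaluable for response". It requires a dose of each drug and "at least 1 dose of pralatrexate and had at least 1 disease assessment", and then points to Section 5.7. The section goes on to apply the stage-1 rule (stop at 0 responses) to the first 7 evaluable patients, of whom up to 6 may come from Phase 1, and sets the stage-2 total at 24. It gives no other definition of evaluable.

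**Synopsis, Phase 2 portion.** Same definition, with neither the exception nor a pointer to 5.7.

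**Section 5.7 (Replacement of Subjects).** For the Phase 2 portion, patients without a tumor response assessment are replaced, "except due to progression of disease prior to the first tumor response assessment". For the Phase 1 portion it lists only missed doses as grounds for replacement.

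**Section 12.3.3 (Analysis of Anti-tumor Activity).** "ORR will be calculated as the proportion of evaluable patients that have confirmed CR or PR". The section covers everyone treated at the RP2D, Phase 1 included. It first asks that the patient received both drugs "and underwent at least one response assessment", and then adds that "patients will be evaluable for efficacy if they discontinued study therapy prior to the first response assessment because of progression of disease".

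**Section 12.2** refers the reader to 5.7 for evaluability in both phases.

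**The concern.** Two definitions of one population stand in the plan, and they differ only in patients whose outcome is already known to be bad. A patient who stops for progression before any assessment is a certain non-responder. Section 12.3.3 counts that patient; 12.1.2, read as written, does not.

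Such patients are plausible. The first on-treatment staging falls in Cycle 4, between Day 15 and Day 21, and the protocol quotes a single-agent median PFS of 3.5 months. Section 12.3.4 itself monitors for progression before three cycles are complete, which is earlier than any scheduled restaging. Section 5.7 encourages, but does not require, imaging when an early progressor stops.

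At stake is the trial's only futility rule. Most of the first 7 can be carried-over Phase 1 patients, and these are the patients for whom the governing sentence lacks the exception and for whom 5.7 does not supply it. If the choice between definitions is left until responses are known, the stop decision becomes data-dependent. The 24 counted under 12.1.2 may also differ from the denominator used in 12.3.3.

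**Working it through.** **1. The plan's own figures (Section 12.1.2).**
- Chance of at least 1 response in 7 at ORR 35%: 1 - 0.65^7 = 0.951. Stated: at least 95%.
- Standard error at n = 24: sqrt(0.30 x 0.70/24) = 9.35% at 30% (and at 70%); sqrt(0.50 x 0.50/24) = 10.2% at 50%. Stated: 9.4%-10.2%.
- Widest exact 95% interval at n = 24: at 12/24, from 29.1% to 70.9%, width 41.8%. Stated: 42%.

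All three reproduce. They condition on 7 or 24 evaluable patients, so the disputed wording does not touch them.

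**2. When the first scan falls.** Cycle 4 Day 1 is day 1 + 3 x 21 = 64, so Cycle 4 Days 15-21 are days 78-84. Assuming exponential PFS with a median of 3.5 months, the share progressed or dead by day 80 is 1 - 2^(-(80/30.44)/3.5) = 0.41. This is only a loose ceiling on the unscanned share, because it includes everyone who was imaged.

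**3. Which rule reaches whom, if there is progression and no assessment.**

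| Patient | 12.1.2 and synopsis, as written | 5.7 | 12.3.3 |
|---|---|---|---|
| Phase 1 at RP2D, carried over | not counted | silent | counted |
| Enrolled in Phase 2 | sentence is about Phase 1 patients; no other definition given | not replaced | counted |

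**4. Effect on the stage-1 stop.** Let p be the true ORR and u the share of treated patients who progress with no assessment. The documents do not give u; 5% to 20% is assumed. If these patients are left out, the expected ORR among those counted is p/(1 - u), and the chance of 0/7 is (1 - p/(1 - u))^7. If they are counted, it is (1 - p)^7.

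Upper illustration, with all of the first 7 under the literal wording:
- p = 29%: counted, 0.71^7 = 9.1%. Left out: u = 5%, (1 - 0.305)^7 = 7.8%; u = 20%, (1 - 0.3625)^7 = 4.3%.
- p = 20%: counted, 0.80^7 = 21.0%. Left out: u = 5%, (1 - 0.2105)^7 = 19.1%; u = 20%, (1 - 0.25)^7 = 13.3%.

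Narrower illustration, with the wording reaching only 6 carried-over patients and each vacated place filled by a Phase 2 patient. Each of the 6 places then yields a non-responder with probability (1 - u - p) + u(1 - p) = 1 - p(1 + u), and the stop probability is (1 - p) x (1 - p(1 + u))^6:
- p = 29%: 0.71 x 0.6955^6 = 8.0% at u = 5%; 0.71 x 0.652^6 = 5.5% at u = 20%.
- p = 20%: 0.80 x 0.79^6 = 19.4% at u = 5%; 0.80 x 0.76^6 = 15.4% at u = 20%.

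**5. A concrete case.** Take six Phase 1 patients at the RP2D, of whom four are scanned non-responders and two are unscanned progressors, followed by one Phase 2 non-responder. Counting early progressors gives 0/7 and termination. Under 12.1.2 as written the count is 0/5, and two more patients are needed; if either responds, the trial goes on.

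**6. The total of 24.** If one carried-over patient is left out of the 24 and then restored by 12.3.3, 8/24 = 33.3% becomes 8/25 = 32.0%.

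**The case against.** A reader might infer that the reported ORR is inflated. The documents do not support this. Section 12.3.3 is the analysis rule for ORR; it names early progressors as evaluable and covers Phase 1 patients at the RP2D. That part of the objection stands in full.

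Two pointers, in 12.1.2 and 12.2, lead to 5.7. For Phase 2 patients this largely settles the matter, because 5.7 says that they are not replaced. It does not settle it for carried-over patients, since the exception in 5.7 is confined to the Phase 2 portion. The synopsis definition has no pointer.

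The Study Calendar (Section 10, footnote r) schedules a PET-CT or CT at end of treatment for patients who stop for progression. A patient who has that scan has a disease assessment and counts as a non-responder even under 12.1.2. This stands, and it makes a large unscanned share less likely. What remains are patients in whom that scan is missed or not feasible. Sections 5.7 and 12.3.3 both provide for patients without an assessment, so the plan itself expects some.

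Finally, applying 5-20% to all of the first 7 goes beyond a sentence written about at most 6 carried-over patients, and the share has no source in the documents. This also stands, so those results are an upper illustration and not an estimate.

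**Conclusion.** Wrong as written: an internal contradiction, minor to moderate. It is not a demonstrated bias in the primary estimate.

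The omission acts on the stage-1 count, chiefly through carried-over Phase 1 patients, and in one direction only: it can lower the chance of a 0/7 stop and cannot raise it. On the upper illustration the loss is 1.3 to 4.8 percentage points at a true ORR of 29% (9.1% to 7.8-4.3%) and 1.9 to 7.7 points at 20% (21.0% to 19.1-13.3%). It is smaller if only the 6 carried-over patients are affected, and nil if every early progressor has the end-of-treatment scan. These sizes rest on the assumed 5-20% unscanned share and on every such patient being a non-responder. The second is true by definition of the group; the first is not in the documents. The secondary effect is that the 24 under 12.1.2 need not equal the denominator in 12.3.3.

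**What to change.** In 12.1.2 and in the synopsis, replace the definition with the one that 12.3.3 amounts to: at least one dose of each drug, and either at least one disease assessment or discontinuation for progression before the first assessment, the latter counted as a non-responder. State that this definition governs the first 7, the total of 24 and Phase 1 patients treated at the RP2D. Settle it before the stage-1 count is made.

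The cost is wording in two places. Sample size, stopping boundary and stated design figures do not change, and neither does the final ORR rule in 12.3.3.

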12.2 Sample size accrual rate

The expected sample size is 30 evaluable patients: 12 during the Phase 1, and 18 additional patients in the Phase 2, assuming 6 patients treated at RP2D during the Phase 1 are also evaluable for response. Between 3-4 high-volume PTCL centers, we expect to accrue 12 patients at COH and 30-36 total in 48 months. The expected sample size may go up to 36 evaluable patients if the higher 2 dose levels are not safe and the lowest dose level is safe (18 in the Phase 1 and 18 in the Phase 2). Patients evaluable/inevaluable for Phase 1/2 portions are described in [Section 5.7](#). Considering replacement of inevaluable patients, the maximum study accrual is set at 40 patients.

12.3 Statistical analysis plan

12.3.1 Demographic and Baseline Characteristics

Patient demographic and baseline characteristics, including age, gender, medical history, and prior therapy, will be summarized using descriptive statistics. For continuous variables, descriptive statistics (number [n], mean, standard deviation, standard error, median (range) will be provided. For categorical variables, patient counts and percentages will be provided.

12.3.2 Toxicity Analysis

Observed toxicities will be summarized by type (organ affected or laboratory determination such as absolute neutrophil count), severity (by NCI CTCAE v5.0 and nadir or maximum values for lab measures), date of onset, duration, reversibility, and attribution.

12.3.3 Analysis of Anti-tumor Activity

This study will aim to obtain an estimate of the anti-tumor activity of the study combination. ORR will be calculated as the proportion of evaluable patients that have confirmed CR or PR, as defined according to the 2014 Lugano Classification, exact 95% confidence intervals will be calculated for these estimates. Response rates will also be evaluated based on number and type of prior therapy(ies). Duration of response, as well as progression-free survival and overall survival will be estimated using the product-limit method of Kaplan and Meier. As secondary endpoints, the ORR and CR rate will also be estimated according to the International Harmonization Project response criteria (Cheson 2007).⁹

Any patient treated at the RP2D, including those from the Phase 1 portion, will be included in efficacy analyses. Patients will be evaluable for efficacy assessment if they received at least one dose of pralatrexate and at least one dose of pembrolizumab and underwent at least one response assessment. As discussed in [Section 5.7](#), patients will be evaluable for efficacy if they discontinued study therapy prior to the first response assessment because of progression of disease rather than solely because of unacceptable toxicity, withdrawal of consent, or investigator's decision.

12.3.4 Safety Analysis and Stopping Rules for Excessive Toxicity or for Rapid Disease Progression

Because of the unique immune-related adverse events (IrAEs) observed with checkpoint inhibitors, we will monitor for "unacceptable toxicity" (defined in [Section 11.2](#)) and treatment-related mortality at any time during study treatment with this new combination of drugs. This monitoring will include all patients treated on the study regardless of the dose levels they were on. The expected rate of "unacceptable toxicity" should not be >33%. If the rate of "unacceptable toxicity" is >33% after at least 6 patients are treated on study at any bi-annual safety review, or if a 2nd death that is at least possibly related to study treatment occurs regardless of the number of patients on study, accrual will be halted and a full review of these events will be performed by the City of Hope Data Safety Monitoring Committee (DSMC). Patient accrual will not resume until approved by the DSMC to do so. These rules are in addition to the bi-annual review of all toxicities submitted to the City of Hope Data Safety Monitoring Committee (DSMC). Patients with ongoing toxicity will be followed until resolution or stability.

In addition, because of the evidence that PD-1 may act as a tumor suppressor in preclinical T-cell lymphoma models and the recent reports of rapid disease progression in patients with ATLL, a subtype of PTCL, we will also monitor for rapid progression of disease. If at any bi-annual safety review during the conduct of the study, and after at least 3 patients are treated on study, > 33% of patients who received at least one dose each of pembrolizumab and pralatrexate (regardless of the dose level or if during the phase 1 or phase 2 portion of the study) experience rapid progression (i.e. an acceleration of disease activity with disease progression according to the 2014 Lugano classification prior to completion of 3 cycles of study therapy), the study accrual will be halted and a full review of these events will be performed by the City of Hope Data Safety Monitoring Committee (DSMC). Patient accrual will not resume until approved by the DSMC to do so.

